## 9.3.3.2.4. Change in UACR

In clinical trials, finerenone has been demonstrated to have beneficial effects on UACR [31,32], and UACR declines of 30% have been associated with favourable long-term kidney outcomes [32-34]. Guidelines for CKD management in patients with T2D recommend targeting 30% reductions in UACR to prevent CKD progression [35]. In this study, the secondary analysis will evaluate the time to a 30% decrease from baseline UACR values during follow-up; additional thresholds (e.g., 50% decline, 70% decline) may also be considered. This analysis will be performed in an analysis set of those with available baseline UACR laboratory values, and recorded UACR laboratory values during follow-up will be used to define the outcomes of interest.

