### 8.2. Secondary objectives

The secondary objectives in this study are the following:

• To estimate the risk of the individual components of a composite cardiovascular outcome (i.e., first occurrence of fatal or nonfatal acute myocardial infarction; first

occurrence of hospitalisation for heart failure) in patients with CKD and T2D initiating finerenone compared with that in patients with CKD and T2D not using finerenone (in the same primary study cohort as the primary analysis).

- To estimate the risk of new-onset heart failure in patients with CKD and T2D initiating finerenone compared with that in patients with CKD and T2D not using finerenone (in a subset of the primary study cohort from which patients with a history of heart failure are excluded).
- To estimate the risk of a decline in UACR (i.e., first occurrence of specific UACR decline thresholds) in patients with CKD and T2D initiating finerenone compared with that in patients with CKD and T2D not using finerenone (in a subset of the cohort of patients with baseline UACR values).
- To assess the safety of finerenone by estimating the risk of hyperkalaemia in patients with CKD and T2D initiating finerenone compared with that in patients with CKD and T2D not using finerenone.
- To estimate the risk of the above mentioned outcomes in clinically relevant subgroups of patients with CKD and T2D initiating finerenone compared with that in patients with CKD and T2D not using finerenone.
- To assess the effectiveness of initiating finerenone and titrating dosage according to the approved label by estimating the risk of outcomes of interest in patients with CKD and T2D initiating finerenone and uptitrating to 20 mg (when recommended) compared with that in patients with CKD and T2D not using finerenone.

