#### 9.2.1.2. Selection criteria

Individuals must meet all the following inclusion criteria on or before Time 0 to be included in the cohort:

- Active registration or continuous enrolment for at least 365 days in the data source before Time 0 (days [-365, 0])
- No recorded use of finerenone before Time 0 (days [-all available, 0])
- Aged 18 years or older on Time 0
- Diagnosis of T2D at any time on or before Time 0 (days [-all available, 0])
- Evidence of CKD on or before Time 0 (days [-all available, 0]), identified by meeting any of the following criteria:
  - A diagnosis code indicating CKD stage 1, 2, 3, 4, or stage unspecified
  - Two UACR test results  $\geq$  30 mg/g separated by at least 90 days and no more than 540 days.
  - Two different eGFR test results  $\geq 15 \text{ mL/min}/1.73 \text{ m}^2 \text{ AND}$ < 90 mL/min/1.73 m^2 [17] separated by at least 90 days and no more than 540 days. If a reported eGFR test result is available in the data, it will be used as recorded to determine eligibility (as that was the eGFR value available to the prescribing clinician at the time of Time 0). If an eGFR value is not reported, but there is sufficient information to calculate the eGFR, it will be calculated using the creatinine-based 2021 CKD-EPI equation [18] (Section 9.3.1).

Individuals will be excluded if they meet any of the following exclusion criteria on or before Time 0:

- Type 1 diabetes (T1D) at any time on or before Time 0 (days [all available, 0]), as finerenone is not indicated for use in T1D
- Evidence of end-stage kidney disease (ESKD) at any time on or before Time 0 (days [all available, 0]) —as finerenone is not recommended to be initiated in individuals with ESKD or severely reduced eGFR—identified as any of the following criteria:
  - Two different eGFR test results < 15 mL/min/1.73 m^2 [17] separated by at least 90 days and no more than 540 days
  - Dependence on dialysis (at least 3 sessions over at least 90 days)
  - A diagnosis code indicating kidney failure or CKD stage 5 (International Classification of Diseases, 10th Revision, Clinical Modification [ICD-10-CM] code N18.5)
  - A diagnosis code indicating having a kidney transplant (ICD-10-CM code Z94.0)
- Diagnosis of kidney cancer at any time on or before Time 0 (days [-all available, 0]), as decreased renal function resulting from kidney cancer may differ in treatment response from diabetic CKD.

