### 9.3. Variables

### 9.3.1. Measures of kidney function

Determining the level of kidney function (i.e., eGFR and CKD stage) is required at numerous points in this analysis to determine study eligibility and define baseline CKD stage. Kidney function may be determined either with eGFR measurements, recorded CKD diagnoses, or UACR measurements.

When required to be calculated from recorded serum creatinine values, eGFR will be calculated using the creatinine-based 2021 CKD-EPI equation (without including cystatin-C) [18,23-27]:

$$eGFR = 142 \times \min\left(\frac{Scr}{\kappa}, 1\right)^{a_1} \times \max\left(\frac{Scr}{\kappa}, 1\right)^{a_2} \times c^{Age} \times d$$

Where:

- $a_1 = -0.241$  for female individuals and -0.302 for male individuals
- $a_2 = -1.200$
- *c* = 0.9938
- d = 1.012 for female individuals and 1 for male individuals
- $\kappa = \text{is } 0.7$  for female individuals and 0.9 for male individuals
- min indicates the minimum of  $\frac{scr}{\kappa}$  and 1, and max indicates the maximum of  $\frac{scr}{\kappa}$  and 1.
- The coefficient  $a_1$  is used for levels of creatinine less than or equal to 0.9 mg/dL for male individuals and 0.7 mg/dL for female individuals.
- The coefficient  $a_2$  is used for levels of creatinine greater than 0.9 mg per decilitre for male individuals and 0.7 mg per decilitre for female individuals.

CKD stage at Time 0 (Section 9.3.3.3) will be defined based on either the most recent eGFR level or recorded diagnosis of CKD stage on or before Time 0. CKD stage based on eGFR categories (mL/min/ $1.73 \text{ m}^2$ ) or diagnosis coding will be defined as follows:

- Stage 1: eGFR  $\geq$  90, normal or high
- Stage 2: eGFR 60-89, mildly decreased
- Stage 3: eGFR 30-59, mildly to severely decreased
- Stage 4: eGFR 15-29, severely decreased
- Stage 5: eGFR < 15 or treatment with chronic dialysis or kidney transplant, ESKD
- Stage unspecified (for individuals with only stage-unspecified CKD diagnosis codes)

Albuminuria will be measured using the most recent UACR [28] value on or during the 365 days before Time 0, and selection criteria will include both eGFR and UACR-based entry definitions of kidney function (Section 9.2.1.2). For those individuals with UACR values

available, the extent of albuminuria will be categorised as follows (UACR mg/g is approximately equivalent to albumin excretion rate mg/d):

- A1: < 30, normal to mildly increased
- A2: 30-300, moderately increased

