- A3: > 300, severely increased
- Unknown, for individuals without baseline UACR values

The UACR categories will be identified if available, as they provide additional information regarding cardiovascular disease risk and kidney prognosis [5], but they will be defined as a separate variable from CKD stage; for CKD staging, only eGFR values or diagnosis codes will be used.

The most recent UACR value on or during the 365 days before Time 0 will be used as the baseline UACR value for the UACR-specific analysis set. Additional UACR laboratory values occurring during follow-up will be identified to define UACR-based outcomes.

Additionally, diagnoses of proteinuria and nephrotic syndrome will be identified. ICD-10-CM diagnosis codes for proteinuria do not indicate stage, and there may be considerable overlap between diagnosis-based measures and the UACR measurements for those with available laboratory values; however, diagnosis-based measures may be used in combination with laboratory test–based measures.

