### 9.7.4.3. Change in UACR

The analysis of change in UACR outcomes will be performed in an analysis set restricted to those with baseline UACR values (Section 9.3.3.2.4). Time to a 30% decline in UACR from baseline will be described in each treatment group with incidence rates and cumulative incidence plots. Time to additional thresholds (e.g., 50%, 70%) may also be evaluated separately. Comparisons of the treatment groups using HRs and 95% CIs may be considered, if feasible; to inform the feasibility of performing comparative analyses, the frequency of UACR testing in each treatment group will be described and evaluated for comparability (to be described in the SAP).

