### 9.7.5.2. Change in UACR values over time

The analysis of change in UACR values over time will be performed in an analysis set restricted to those with available baseline UACR values (Section 9.3.3.2.4). Recorded UACR values during follow-up will be identified and used to estimate change in UACR values from baseline at 4 months and 12 months after the Time 0 with pattern-mixture models [61]. The factors considered as censoring criteria for the other, time-to-event outcomes will be used to define loss-to-follow-up for these analyses.

Descriptive analyses of UACR over time at 4 months and 12 months will be performed in each treatment group. Comparisons between groups may be considered, if feasible, based on descriptive analyses of UACR testing frequency between treatment groups (Section 9.7.4.3; further details to be provided in the SAP).

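### The secondary UACR outcome counts any first recorded 30% fall from a single baseline value, normal albuminuria included, so a substantial share of events can be measurement noise and testing frequency

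*Protocol*

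**What the plan says.** Section 8.2 sets a secondary objective on the "first occurrence of specific UACR decline thresholds", comparing finerenone initiators with non-users. Section 9.3.3.2.4 makes this concrete: "the secondary analysis will evaluate the time to a 30% decrease from baseline UACR values during follow-up". Follow-up values are whatever laboratory results were recorded; there is no testing schedule. Falls of 50% and 70% are optional extras.

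The same section defines the set: "This analysis will be performed in an analysis set of those with available baseline UACR laboratory values". Section 9.3.1 fixes the baseline: "The most recent UACR value on or during the 365 days before Time 0 will be used as the baseline UACR value". It is a single value that may be up to a year old.

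Nothing keeps normal albuminuria out. Section 9.3.1 has the category "A1: < 30, normal to mildly increased", and section 9.2.1.2 lets a patient enter with "A diagnosis code indicating CKD stage 1, 2, 3, 4, or stage unspecified" or on eGFR results, with no albuminuria needed.

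On analysis, section 9.7.4.3 says: "Time to a 30% decline in UACR from baseline will be described in each treatment group with incidence rates and cumulative incidence plots". Hazard ratios are optional, after UACR testing frequency in each group has been described and judged comparable, with detail left to the SAP. Section 9.3.4 lists baseline albuminuria as a stage covariate.

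**The concern.** The event is a ratio of two single measurements of a variable analyte, and the first crossing counts. That has three consequences.

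- Random variation alone produces crossings, and each further test is another opportunity. The group tested more often shows more declines even if nothing has changed.
- In patients below 30 mg/g a 30% fall stays within the normal category. Section 9.3.3.2.4 justifies the threshold by kidney outcomes and by guideline targets for preventing CKD progression; it gives no separate reason for applying it to normal values.
- Staging baseline UACR into three classes, the top one open-ended above 300 mg/g, leaves room for the groups to differ within a stage. If initiators tend to have higher readings within a stage, regression to the mean would add declines in that group.

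At stake is whether the group-specific rates and curves for this secondary outcome can be read as an effect on albuminuria.

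**Working it through.** The protocol gives no event rate, within-person variability or test count for this outcome, so there is no figure to reproduce. The check sizes the effect under stated assumptions.

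**From the protocol:** threshold ratio 0.70; one baseline value; first crossing counts. **Assumed:** log-normal within-person variation, independent values, CV of 20% to 50%, 1 to 4 follow-up tests.

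**Formulas.** Log-scale SD: s = √ln(1 + CV²). With no true change, the chance that one follow-up value is at or below 0.70 × baseline is Φ(ln 0.70 / (s√2)). At CV 30%, s = 0.294, s√2 = 0.415, ln 0.70 = −0.357, z = −0.859 and the probability is 0.195. For k tests sharing one baseline, average 1 − [1 − Φ(ln 0.70/s + z)]^k over a standard normal z.

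**Proportion with an event when nothing has changed**

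| CV | 1 test | 2 tests | 3 tests | 4 tests | Risk ratio, 2 v 1 tests |
|---|---|---|---|---|---|
| 20% | 10% | 17% | 22% | 26% | 1.67 |
| 30% | 20% | 31% | 38% | 44% | 1.57 |
| 40% | 26% | 39% | 47% | 53% | 1.51 |
| 50% | 30% | 44% | 53% | 59% | 1.48 |

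**Share of events that noise could explain.** Give one group a true 30% fall and divide the no-change probability by that group's event probability, over 1 to 3 tests:

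- CV 20%: 0.20 to 0.30
- CV 30%: 0.39 to 0.51
- CV 40%: 0.51 to 0.63
- CV 50%: 0.59 to 0.70

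At CV 30% with one test, for example, 0.195 / 0.500 = 0.39.

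**Would confirmation at the next recorded value cure it?** With two tests and no change, false events at CV 30/40/50% fall from 31/39/44% to 8/12/15%. The dependence on testing grows: for 3 against 2 tests the spurious risk ratio is 1.24/1.22/1.20 with a single value and 1.44/1.38/1.36 with confirmation. A patient with only one follow-up test can never have a confirmed event.

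**Reach of the testing check.** In section 9.7.4.3 it decides whether hazard ratios are produced. The rates and cumulative incidence plots by group are planned whatever it shows. It does not address noise under equal testing, which raises both curves and dilutes the contrast, or normal baselines.

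**The case against.** The strongest defence is that the protocol already sees the testing problem: sections 9.7.4.3 and 9.7.5.2 make group comparisons conditional on UACR testing frequency. This stands for the hazard ratio, so a reader should not infer that the plan ignores testing frequency or that the objective is beyond answering. It does not cover the rates and curves.

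A reader might also infer that most counted declines are noise. The documents do not support that. The share depends on CV, test counts and true effect, none of which is given; at CV 20% with a true 30% fall it is under a third.

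Section 9.7.6 lists UACR level at Time 0 as a subgroup, which could separate normal baselines. It yields hazard ratios where feasible and leaves the main set unchanged. It is also fair that the 30 mg/g cut in section 9.2.1.2 is one of several CKD entry routes, and that a floor narrows the broad population the study wants. Keeping the all-baseline set as sensitivity meets this.

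No section says that initiation follows a high UACR, so regression to the mean in the finerenone group is a possibility and not a finding.

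Finally, section 9.7.5.2 says recorded values will be "used to estimate change in UACR values from baseline at 4 months and 12 months". One might read this as analysis of untransformed, skewed data, but the section fixes no scale, and the SAP may set one. No criticism is made there.

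The unseen SAP could add a floor or a confirmation rule. As the protocol stands, though, the event and the set are stated without either.

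**Conclusion.** The point holds for the definition and the analysis set. The protocol fixes the event as the first recorded fall of 30% from one baseline value, in anyone who has one. With no true change, 10% to 30% of patients would meet it at one retest and 17% to 44% by two, and two tests against one would give a spurious risk ratio of about 1.5 to 1.7. These figures rest on an assumed CV of 20% to 50%, log-normal variation and independent values. They support saying that a substantial share of events can be noise and testing frequency; they do not fix that share. This is one secondary outcome, and the primary analysis is untouched.

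**What to change.** 1. Make baseline UACR of at least 30 mg/g the main UACR analysis set, and keep all baseline values as a sensitivity analysis.
2. In the propensity model for this set, use continuous log baseline UACR in place of the A1/A2/A3 stage alone. Every patient in the set has the value. This balances baseline differences within a stage and the regression to the mean that would follow from them.
3. Report a decline confirmed at the next recorded UACR only as a sensitivity analysis, among patients with at least two follow-up values. It lowers absolute false events but raises relative dependence on testing frequency, so it should not become the main definition.

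The cost is a change of wording, a smaller analysis set and fewer events. The floor makes the event meaningful but does not reduce measurement noise in the patients kept, so the curves should be read beside the testing-frequency description that section 9.7.4.3 already plans.

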### 9.3.3.2.5. Hyperkalaemia

Hyperkalaemia is listed in the warning and precautions section of the US and EU labels as a potential concern associated with finerenone use [13,22]. The secondary safety outcome of hyperkalaemia will evaluate the first occurrence of a hospitalisation or emergency department visit with a diagnosis code for hyperkalaemia [36] during follow-up.

As part of the study's selection criteria, individuals with a recent diagnosis of hyperkalaemia or elevated serum potassium will be excluded (Section 9.2.1.2), as finerenone initiation is not recommended in those with elevated serum potassium [16]. Thus, no additional outcome-specific exclusion criteria will be applied to the analysis of hyperkalaemia. Estimates of

hyperkalaemia incidence in secondary healthcare databases may vary widely depending on the operational definition used or the reference range for the serum potassium level at that laboratory [37,38].

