### 9.3.2.1. Finerenone initiation treatment strategy

The treatment strategy evaluated by this study will be initiation and continuing use of finerenone. Deviation from the treatment strategy will be defined as discontinuation of finerenone for reasons other than elevated potassium or ESKD, which is consistent with the label and treatment recommendations.

Finerenone initiation will be defined as the first observed finerenone prescription during the study period. For the primary analysis, finerenone initiators will be permitted to up-titrate or down-titrate dosages while remaining adherent to the treatment strategy. Guidelines allow for pauses in finerenone treatment after the occurrence of elevated serum potassium [13]; thus, gaps in use or discontinuation of finerenone after an elevated serum potassium laboratory measurement or diagnosis of hyperkalaemia will not be considered deviation from the

treatment strategy. Additionally, the European Union (EU) label explicitly calls for discontinuation of finerenone in ESKD [22]; thus, discontinuation for ESKD will not be considered deviation from the treatment strategy.

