### 9.3.2.3. Finerenone initiation and titration treatment strategy

As a secondary analysis, an additional treatment strategy will be evaluated in which patients are required to initiate finerenone and up-titrate to the target daily dosage of 20 mg, per the approved US label [13]. Patients using this treatment strategy will be identified at finerenone initiation (either at 10 mg or 20 mg). Among those who initiate finerenone at 10 mg per day, failure to up-titrate to 20 mg per day by 10 weeks after initiation (more than twice the recommended 4-week period) will be considered deviation from the treatment strategy (unless serum potassium levels are greater than 4.8 mEq/L, as the US label instructs maintaining the 10-mg daily dosage). Those who initiate finerenone at 20 mg per day will be considered adherent to the treatment strategy. Subsequent down-titration back to 10 mg will be allowed, consistent with allowed dose adjustments [13].

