#### 9.3.3.1. Primary composite cardiovascular outcome

The primary composite cardiovascular outcome will evaluate the first occurrence of any of the following events during follow-up:

- An inpatient hospital diagnosis of fatal or nonfatal acute myocardial infarction [29]
- An inpatient hospitalisation with a primary diagnosis of heart failure [30]

Individuals with prior cardiovascular events are eligible for finerenone treatment; thus, those with an occurrence of these events before Time 0 may be included in the overall study cohort (before application of outcome-specific exclusion criteria). However, to ensure identification of cardiovascular outcomes that newly occur after Time 0, analysis of this composite cardiovascular outcome will be performed in an analysis set that also excludes individuals with an acute myocardial infarction diagnosis in the 365 days before Time 0. Those with a history of heart failure will be included in the analysis, and history of heart failure will be included.

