  - Atherosclerosis
  - Atrial fibrillation
  - Cerebrovascular disease (stroke or transient ischaemic attack)
  - Congestive heart failure
  - Hypercholesterolaemia
  - Hyperlipidemia
  - Hypertension
  - Peripheral vascular disease
  - Unstable angina
- Other components of the Charlson Comorbidity Index or similar comorbidity score [48,49] (as single entities, not listed elsewhere)
  - Anaemia
  - Chronic obstructive pulmonary disease
  - Congestive heart failure
  - Dementia

- Human immunodeficiency virus
- Liver disease
- Malignancy other than kidney cancer or nonmelanoma skin cancer
- Paralysis
- Other comorbidities
  - Coronavirus disease 2019 (COVID-19) diagnosis
  - Hyperkalaemia (history of hyperkalaemia, more than 90 days before Time 0)
  - Osteoporosis
  - Pneumonia

The following lifestyle cardiovascular factors will be defined, as available in the data:

- Body mass index or evidence of obesity
- Smoking status
- Alcohol abuse

The following healthcare utilisation measures will be identified in the 365 days before and including Time 0 to characterise patients' healthcare access, healthcare-seeking behaviour, and indicators of disease state at the time of index medication initiation:

- Healthcare utilisation
  - Hospital visits and hospital admissions
  - Emergency department visits
  - Long-term care or skilled nursing facility residence
  - Number of eGFR laboratory tests performed
  - Number of serum potassium laboratory tests performed
- Preventive health services
  - Influenza vaccination
  - Pneumococcal vaccination
  - COVID-19 vaccination
  - Bone mineral density test
  - Screening mammogram
  - Other cancer screening
- Frailty indicators [50]
  - Arthritis
  - Bladder dysfunction
  - Dementia
  - Psychiatric illness
  - Weakness
  - Vertigo

The following comedications will be identified in the 183 days before and including Time 0 to characterise individuals' recent treatments and indicators of disease state at the time of index medication initiation:

- Medications for T2D
  - Alpha glucosidase inhibitors
  - Dipeptidyl peptidase-4 inhibitors (DPP-4i)
  - GLP-1 RA
  - Meglitinides
  - Metformin
  - SGLT2i
  - Sulfonamides
  - Sulfonylureas
  - Thiazolidinediones
  - Insulin
- Cardiovascular medications
  - Angiotensin-converting enzyme inhibitors/angiotensin receptor blockers (ACEi/ARBs)
  - Aldosterone receptor blockers
  - Angiotensin receptor-neprilysin inhibitor
  - Anticoagulants

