### 9.7.4.4. Hyperkalaemia

The analysis of hyperkalaemia will be estimated in the overall study population without any outcome-specific exclusion criteria (Section 9.3.3.2.5). Treatment group–specific incidence rates will be estimated following the same methods as those for the primary outcome (Section 9.7.3).

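### Potassium testing after Time 0 may differ between arms, and the protocol plans no check of this for hyperkalaemia, its only designated safety comparison

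*Protocol*

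**What the plan says.** Section 8.2 sets the objective: "To assess the safety of finerenone by estimating the risk of hyperkalaemia in patients with CKD and T2D initiating finerenone compared with that" in nonusers. No other objective is worded as assessing safety. Section 9.3.3.2.5 defines the outcome, which "will evaluate the first occurrence of a hospitalisation or emergency department visit with a diagnosis code for hyperkalaemia". It states neither a diagnosis position nor a confirming potassium value. The heart failure part of the primary outcome in Section 9.3.3.1 is narrower: "An inpatient hospitalisation with a primary diagnosis of heart failure".

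Potassium enters the finerenone strategy in two places. Section 9.3.2.1 keeps a patient adherent through interruptions that follow a high potassium: "Guidelines allow for pauses in finerenone treatment after the occurrence of elevated serum potassium". Section 9.3.2.3, for the secondary titration strategy, excuses failure to up-titrate by week 10 "unless serum potassium levels are greater than 4.8 mEq/L, as the US label instructs maintaining the 10-mg daily dosage". The comparator strategy in Section 9.3.2.2 has no potassium element.

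Section 9.3.4 lists "Number of serum potassium laboratory tests performed" as a covariate, measured in the 365 days up to and including Time 0. For UACR, Section 9.7.4.3 says that "the frequency of UACR testing in each treatment group will be described and evaluated for comparability", and uses the result to judge whether a comparison is feasible. For hyperkalaemia, Section 9.7.4.4 says only: "The analysis of hyperkalaemia will be estimated in the overall study population without any outcome-specific exclusion criteria", with rates estimated by the primary outcome's methods.

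**The concern.** A coded hyperkalaemia visit can arise in two ways. The patient presents unwell, or a laboratory result leads to a referral or to an additional code during a visit. The second route depends on how often potassium is measured. If starting finerenone itself prompts more testing, users can accumulate more coded events than nonusers at the same underlying risk. That part of the contrast is not harm from the drug.

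This matters because it is the only comparison designated as safety, and at least 20,000 initiators are expected (Section 9.5). A modest detection difference could then give a narrow interval around a mixed quantity, with nothing in the planned output to warn the reader.

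**Working it through.** **1. The plan's own figures.** Section 9.5 sizes only the primary composite. With RR 0.86 and a 10:1 ratio, a pooled two-proportion calculation gives 83.2% at 30,000 records (14.4% risk) and 80.2% at 60,000 (7.2% risk), which agrees with the stated figures. A log-RR Wald calculation gives 81.2% and 78.5%. The protocol gives no event risk, testing rate or precision for hyperkalaemia, so the size of any detection bias cannot be derived from it.

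**2. Do the planned safeguards reach testing after Time 0?**
- *Baseline weights (9.3.4, 9.7.2):* potassium tests are counted up to Time 0 only. Weighting on them cannot remove a difference that begins with treatment.
- *Censoring weights (9.7.3):* these address selective loss from follow-up, not detection of the outcome.
- *Negative controls (9.7.7.1):* the candidates are asthma visits and hand or finger laceration. Neither is found by measuring potassium.
- *Limitations (9.9):* outcome misclassification is mentioned in general terms, but not a difference in detection between arms. Section 9.3.3.2.5 cautions about the operational definition and laboratory reference range only.
- *Testing-frequency check:* planned for UACR in 9.7.4.3 and again in 9.7.5.2; absent from 9.7.4.4.

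**3. Is a between-arm comparison really planned?** Section 9.7.4.4 names only incidence rates. But the objective in 8.2 is comparative, the primary methods in 9.7.3 include a hazard ratio, and 9.7.6 plans hazard ratios in a subgroup reserved for hyperkalaemia (potassium-sparing diuretic use). So yes.

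**4. Illustration; every input is an assumption.** Let s be the share of nonuser events that are test-triggered visits, and k the user-to-nonuser ratio of such visits. With no true effect, the apparent rate ratio is 1 − s + s·k:

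| s | k = 1.5 | k = 2 | k = 3 |
|---|---|---|---|
| 10% | 1.05 | 1.10 | 1.20 |
| 20% | 1.10 | 1.20 | 1.40 |
| 40% | 1.20 | 1.40 | 1.80 |

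**5. Would a small ratio show up?** Take 20,000 users and 200,000 comparator records (10:1), true RR 1, and observed RR d produced by detection alone. The probability that the 95% CI lies wholly above 1 is Φ(ln d / SE − 1.96), where SE² = (1−p1)/(n1·p1) + (1−p0)/(n0·p0) and p1 = d·p0. For an assumed p0 = 2% and d = 1.10:
- SE² = 0.978/440 + 0.98/4,000 = 0.002468, so SE = 0.0497.
- ln 1.10 / SE = 0.0953/0.0497 = 1.92.
- Φ(1.92 − 1.96) = 48%.

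At assumed risks of 1% and 5% the result is 27% and 87%. At d = 1.25 it is 92%, above 99% and about 100% for risks of 1%, 2% and 5%. This ignores weighting and repeated comparator Time 0s, both of which would normally widen the interval.

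**The case against.** The case on the other side is substantial, and much of it stands.

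- **Users on a fixed schedule, nonusers unchecked.** A reader might infer this, but no section states a monitoring schedule. The 4.8 mEq/L rule defines deviation for the secondary titration strategy only; under the primary strategy dose changes are free. Comparators are patients with CKD and T2D, have baseline potassium tests counted too, and meet the same 90-day potassium exclusion. The documents support only that testing may differ.
- **Admissions avoided by pausing as downward bias.** A reader might infer this as well. Sections 8, 9.2.1.3 and 9.3.2.1 make label-consistent use, including interruption for high potassium, part of the strategy under study. Admissions prevented that way belong to its effect. Likewise, some extra detected events may be real drug-induced rises in potassium.
- **The UACR parallel is imperfect.** A UACR decline cannot occur without a test, whereas hyperkalaemia needs a hospital or emergency department encounter. This already excludes outpatient laboratory-only detection. It reduces the bias but does not remove test-prompted referrals or incidental codes.
- **Diagnosis position.** Silence is not a decision to accept any position. Section 9.1 leaves operational definitions to the SAP, and the AMI and new-onset heart failure outcomes do not state a position either.
- **The SAP may add the testing table.** It may. But Section 9.7.4.3 flags the UACR check and defers its details to the SAP, while Section 9.7.4.4 flags nothing for potassium.

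It is also tempting to make inpatient events alone the basis of the hazard ratio. That would demote genuine emergency-department-treated harm in the only safety outcome, and the documents give no reason to do so.

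**Conclusion.** The point holds in a limited form. Potassium-linked treatment decisions exist in one arm only, the outcome can be influenced by testing, and none of the planned adjustments or diagnostics would reveal a testing difference that arises after Time 0. The protocol recognises testing frequency as a comparability issue for UACR but provides no equivalent for potassium.

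The documents do not show that a difference exists, nor how large it would be. The ratios of 1.05 to 1.80 and the probabilities above rest wholly on assumed shares, ratios and risks, and model only more testing in users. They show that a modest difference could matter at this sample size, not that it will. Nor do the documents support saying that the hyperkalaemia contrast is uninterpretable. They support saying that it needs a testing description beside it before it is read as drug harm. This is a cheap improvement, not a flaw that invalidates the analysis.

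**What to change.** 1. Keep the combined hospitalisation or emergency department outcome of Section 9.3.3.2.5 as the main definition.
2. In Section 9.7.4.4, add a table of potassium tests per person-year after Time 0 by arm, overall and in the first 3 months. State that the between-group comparison will be qualified if these differ, mirroring Section 9.7.4.3.
3. Add sensitivity analyses less open to surveillance: inpatient events reported separately from emergency department visits, and a version requiring the hyperkalaemia code in the primary position, as Section 9.3.3.1 does for heart failure.
4. In Section 9.9, name differential detection of hyperkalaemia as a limitation, noting that pauses for high potassium are part of the strategy and are not counted as bias.

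The cost is some protocol or SAP wording, one table and two extra outcome definitions, using data types that the protocol already plans to use. The narrower definitions will have fewer events and wider intervals. The testing table informs interpretation; it does not correct the estimate.
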